4.4.2.2. Gestational Age Questionnaires

Once a month, PregSourceSM will send each participant an email, text, or app push notification, with a link to a new questionnaire relevant to her current week of gestation. For example, at 25 weeks of gestation, we may ask whether she has felt her baby move yet. At the end of each questionnaire, if the participant has not entered data into the health trackers in the past month, she will be taken to the appropriate trackers to enter information. This process will allow PregSourceSM to reduce duplication of questions, and capture changes over time in a consistent manner (e.g., all weight data will be entered into the Weight tracker).

If a participant does not complete her monthly questionnaire, she will receive a reminder once a week to do so via email or text to review the information she has entered into the database and provide any appropriate updates to her information.

Gestational-age questionnaires will continue monthly through pregnancy and then quarterly up to 36-months post-partum to capture information on maternal recovery and neonatal and infant outcomes and development.

4.4.2.3. Sub-group Questionnaires

Based on answers to previous questions, a participant with a special condition or complication may be asked to complete additional questionnaires. Such questionnaires will collect more detailed information about her health history, current pregnancy status, and special challenges and issues. Sub-groups may include women with:

- Disabilities (physical or intellectual)
- Obesity
- Lupus or other autoimmune diseases
- Diabetes or gestational diabetes

Sub-group questionnaires will be submitted to the IRB for approval prior to being launched.

4.4.2.4. Future Modules

PregSourceSM is intended to evolve over time with the investigators reviewing, revising, and adding questions, questionnaires, and interactions based on new topic areas and feedback received as well as results collected.

For example, we envision a future module on mental health issues in pregnant and post-partum women. Such a component needs to be carefully planned and implemented to be sensitive to participants' perceptions and to provide meaningful sources of intervention, as needed, for participants whose answers indicate they may be in need of immediate clinical assistance. We would first analyze the results obtained from the Mood Tracker to see how many women require notifications about negative affect. We would, then, consult with experts on post-partum depression and other relevant mental health issues to develop questionnaires and follow-up procedures. As part of that plan, we anticipate conducting beta-testing of any new questionnaires and the follow-up procedures that assure participant safety.

We will submit plans for any future modules to the IRB for review prior to beta testing and module implementation.

4.4.3. End of Participation

Unless she withdraws from the study, a participant ends her participation in the study when her pregnancy ends due to termination, miscarriage, or stillbirth, or at 36-months post-partum. She may, however, choose to continue entering data through subsequent pregnancies.

4.4.4. Follow-up

A participant will not be required to undergo any follow-up medical examinations or doctor's visits. To prompt her to enter information throughout her pregnancy, including pregnancy and newborn outcomes, PregSourceSM will send each participant regular email, text, and/or app push notification reminders, asking her to update her information.

4.4.5. Other Clinical Trials and Studies

No participant will be required to take part in any other research protocol(s), and may continue to participate in PregSourceSM whether she does or does not participate in any other protocol(s).

As part of her account profile, each participant will indicate whether she would like to be contacted to participate in other clinical trials and studies. She will be able to change her Contact and Sharing Preferences at any time in her online Account Profile.

Research investigators for other clinical studies and trials can submit an IRB-approved protocol request to the PregSourceSM Coordinator to recruit participants for their studies. The Operations Committee or its designees will review each proposal. If approved, the Database Administrator will develop an automated search for each protocol to regularly search the data of each registered and interested participant and compare it to the eligibility criteria for the protocol.

Positive search results will be sent to the Coordinators, who will verify the eligibility and send each interested and eligible participant information on how to contact the protocol investigator, if she chooses to do so.

Researchers and physicians will not have access to personally identifiable information (PII) for any participants, nor will they be able to contact participants directly. Studies external to the registry would consent participants separately, based on each study's IRB requirements.

4.4.6. Beta Testing

PregSourceSM will not implement a pilot project. Prior to launching the main PregSourceSM website, app, questionnaires, and trackers, however, we will conduct beta-testing of the website and app, in which beta testers will enter data into PregSourceSM and, in addition, answer questions about the surveys and trackers, their usability, and the process and flow of the tool. We anticipate at least 30 beta testers identified from our Partner organizations will participate.

At the request of the IRB, during the beta test, and after obtaining appropriate informed consent, all pregnant or recently pregnant beta-testers (N=10-20) will be asked to provide us with a copy of their antepartum medical records, so that we can compare their data responses in PregSourceSM to key variables in their medical record for verification. Variables for validation may include:

- Age
- Current pregnancy status
- Pre-pregnancy weight
- Pregnancy weight gain (for women who have delivered)
- Number of previous pregnancies
- History of diabetes
- History of chronic hypertension
- History of prior preterm pregnancies
- Estimated due date for the current pregnancy

These variables are chosen because of their general importance to obstetric care and outcomes and because they are very likely to be recorded in an obstetric medical record. Because many of our beta testers will be pregnant at the time of the test, to validate items from all of them we will need to limit most of the variables to those available early in gestation – excluding outcome variables or variables such as diagnosis of gestational diabetes that are identified at later gestational ages. For those who have delivered, we will also evaluate pregnancy weight gain, an objective measure that can be validated using medical records.

In consultation with biostatisticians in the NICHD Division of Intramural Population Health Research (DIPHR), we will calculate kappa (κ) statistics to quantify agreement between the baseline questionnaire data and the obstetric record. A $\kappa \geq 0.61$ will be considered substantial to excellent agreement (Landis JR and Koch GG 1977).

SECTION 5. STORAGE OF DATA AND SAMPLES

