2.3.1. Primary Outcome Measures

- Gestational age of delivery
- Birthweight of baby
- Maternal gestational weight gain
- Health of baby and mom

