4.4.2. Account Profile Set up and Health History Questionnaire

Once registered and consented, a participant can begin to enter information after reading the PregSourceSM Privacy Policy and Terms and Conditions of use, then completing her Account Profile and taking an initial Health History questionnaire to collect data on:

- Contact information and preferences (email, text, etc.), including an optional alternate contact²
- Demographics and socioeconomic -- NIH-required race/ethnicity data, general family income ranges, education levels

² Alternate Contacts will be contacted only in cases when repeated attempts to gather final pregnancy outcome information have been unsuccessful.

- Interest in participating in a clinical trial. The participant will be asked for her consent to allow the PregSourceSM coordinators to contact her regarding future opportunities for participation in a clinical trial or research study.
- Pre-pregnancy general health – height, weight, a checklist for chronic conditions (e.g., diabetes, lupus), medications
- Reproductive health – contraceptive use, previous pregnancy histories, infertility, use of assisted reproductive technologies
- Current pregnancy health – gestational age, number of fetuses, date of first prenatal visit, prenatal visits completed, any diagnoses received or test results.

A participant will access PregSourceSM questionnaires online and/or via a mobile app to enter her own data. She will be able to download apps (e.g., via the iTunes or Android online app stores) to a smartphone or tablet, and connect these to her online account.³ The apps, as well as the Website, will let her access and enter data into online surveys and trackers. A participant will also be sent reminders and push notifications, asking her to update her information.

All questionnaires will be constructed using “Smart Survey Design” – i.e., using conditional or skip logic to add or skip questions that are not relevant, based on previous answers. Aggregated data will help us analyze response frequencies for survey questions.

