4.4.2.1. Trackers

Each participant can enter data in a set of health “trackers” – online or in-app software diaries that capture daily or weekly information over the course of pregnancy about her weight, nausea symptoms, mood, and sleep. Additional trackers may be added at a later date for tracking nutrition, exercise, and pain. She can enter data in the trackers as often as she chooses. We anticipate that for trackers such as nausea, sleep, and mood, a participant might enter data on a daily basis; while weight data might be entered only once a week or even once a month. Most trackers will collect data on timing, duration, severity/intensity, and related issues. A 2013 report by Citrix⁴, a software company that tracks app usage, shows pregnancy related apps to have wider usage. Many of the available trackers have been used and/or validated in the pregnant population⁵. Recent research articles⁶ have demonstrated the use of web-based methods to collect relevant health related information from pregnant women.

Unless otherwise indicated in her Account Profile, a participant will be reminded on a weekly basis to update her information, if she has not entered new data within the past two weeks.

³ Participants will not be required to use the apps. The apps will be available as a potentially more readily available means of accessing the questionnaires and trackers.

⁴ Nick Bilton, New York Times, August 26, 2015

⁵ Hämeen-Anttila K, Nordeng H, Kokki E, Jyrkkä J, Lupattelli A, Vainio K, Enlund H. Multiple information sources and consequences of conflicting information about medicine use during pregnancy: a multinational Internet-based survey. *J Med Internet Res.* 2014 Feb 20;16(2).

⁶ Wise LA, Mikkelsen EM, Rothman KJ, Riis AH, Sørensen HT, Huybrechts KF, Hatch EE. A prospective cohort study of menstrual characteristics and time to pregnancy. *Am J Epidemiol.* 2011 Sep 15;174(6):701-9

We anticipate including the following trackers:

Weight tracker. Weight would likely be entered weekly/monthly. Data collected includes:

- Weight (in pounds or kilograms)⁷

Nausea tracker. The Nausea Tracker could be entered as often as necessary, collecting data on:

- Date
- Timing (morning, afternoon, all day)
- Duration
- Severity (just nauseous, vomited)

Sleep tracker. In addition to asking about a participant's sleep patterns and apnea diagnosis prior to pregnancy in the initial health questionnaire, the Sleep Tracker may collect data on:

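### Section 4.4.6 names only kappa to check self-report against records, yet age, pre-pregnancy weight and due date are continuous and need a signed difference in their own units

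*Protocol*

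**What the plan says.** Section 4.4.6 (Beta Testing) describes a pre-launch verification, done at the IRB's request, in which "all pregnant or recently pregnant beta-testers (N=10-20) will be asked to provide us with a copy of their antepartum medical records". The list of items opens with "Variables for validation may include", so it is a list of candidates. It mixes yes/no items (current pregnancy status; histories of diabetes, chronic hypertension and prior preterm pregnancy), a count (previous pregnancies) and continuous items (age, pre-pregnancy weight, estimated due date). Weight gain is added for one subset: "For those who have delivered, we will also evaluate pregnancy weight gain, an objective measure that can be validated using medical records".

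The only analysis named is kappa "statistics to quantify agreement between the baseline questionnaire data and the obstetric record", to be calculated in consultation with biostatisticians. A value of at least 0.61 "will be considered substantial to excellent agreement". The section states no weighting, grouping, tolerance, mean difference or interval.

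Pre-pregnancy weight comes from the initial questionnaire (section 4.4.2: "height, weight, a checklist for chronic conditions (e.g., diabetes, lupus), medications"). Later weights are entered by the participant in the Weight tracker (section 4.4.2.1: "Weight would likely be entered weekly/monthly"). Section 2.3.1 lists "Maternal gestational weight gain" as a primary outcome measure.

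**The concern.** Kappa measures agreement between categories, corrected for chance, and has no units. It suits the yes/no histories. A weight, a date or an age must first be turned into categories, or the disagreements weighted, and the resulting kappa depends heavily on how that is done. Even a weighted kappa, which does respond to error size, does not express the error in kilograms or days or show which way it runs. A systematic misreport can therefore earn the favourable label.

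The item with most at stake is pre-pregnancy weight, the starting point for gestational weight gain. Weight gain is itself checked against records, but only in testers who have delivered, and the section expects many testers to be still pregnant. For those women the baseline comparison is the only check on weight, and a kappa would not show whether it is systematically off.

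A secondary point concerns the yes/no histories. With 10 to 20 women, kappa may be undefined or very imprecise if the conditions are uncommon among testers. The protocol gives no prevalence.

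**Working it through.** The protocol has no calculated figure to reproduce: 0.61 is a cited label, and 10 to 20 is a head count with no precision calculation. The numbers of testers and the 0.61 come from section 4.4.6. Every other input below is an assumption.

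**Loss of sign, without simulation.** With quadratic weights, kappa = 1 − (s_d² + d̄²)/(s_x² + s_y² + d̄²), where d̄ is the mean difference, s_d² the variance of the differences, and s_x², s_y² the variances of the two sources (divisor n). The mean difference enters only as a square, so over- and under-reporting of equal size cannot be told apart.

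**Due date example.** Take 20 recorded dates 10 days apart (variance 100 × (20² − 1)/12 = 3,325) and shift every self-report by the same amount.
- Unweighted kappa on exact dates: no pair matches and no match is expected by chance, so kappa = (0 − 0)/(1 − 0) = 0 whether the shift is 1 day or 14.
- Quadratic weights: 1 − 1/(6,650 + 1) = 0.9998 for 1 day, and 1 − 196/(6,650 + 196) = 0.971 for 14 days.

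The same two-week error scores 0 or 0.97, depending on a choice the protocol does not state.

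**Pre-pregnancy weight, simulated.** Assumptions: BMI normal, mean 27, SD 6.5 (floor 15); height mean 1.63 m, SD 0.07 m; self-report = record + bias + normal error, SD 0.9 kg unless stated. The same women are scored as whole-pound unweighted kappa (an extreme reading), unweighted kappa on BMI classes cut at 18.5/25/30, and whole-pound quadratic-weighted kappa. An undefined kappa counts as not reaching 0.61.

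Mean kappa by scoring, n=20:

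| Bias | Whole pounds | BMI class | Quadratic |
|---|---|---|---|
| none | 0.18 | 0.94 | 0.998 |
| −2 kg | 0.01 | 0.84 | 0.99 |
| +2 kg | 0.01 | 0.85 | 0.99 |

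Share of samples in which BMI-class kappa reaches 0.61:

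| Under-report | n=20 | n=10 |
|---|---|---|
| 0 kg | 100% | 99% |
| 1 kg | 99.8% | 98% |
| 2 kg | 98% | 91% |
| 3 kg | 90% | 79% |

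The quadratic version reaches 0.61 in about 100% of samples throughout. With BMI mean/SD of 25/5 or 29/7 and a 2 kg bias, BMI-class mean kappa is 0.80 to 0.86.

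**Mean difference on the same records.** The 95% half-width is t(0.975, n−1) × SD/√n, which is 0.47 SD at n=20 and 0.72 SD at n=10. For a 2 kg bias:

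| Error SD | BMI-class mean kappa (n=20 / n=10) | Half-width, kg (n=20 / n=10) | CI excludes zero (n=20 / n=10) |
|---|---|---|---|
| 0.9 kg | 0.84 / 0.84 | 0.4 / 0.6 | 100% / 100% |
| 2 kg | 0.82 / 0.82 | 0.9 / 1.4 | 99% / 80% |
| 3 kg | 0.78 / 0.77 | 1.4 / 2.1 | 80% / 46% |

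Each limit of agreement has a half-width of t × √(1/n + 1.96²/(2(n−1))) error SDs: 2.262 × √(0.100 + 0.213) = 1.27 at n=10, and 2.093 × √(0.050 + 0.101) = 0.81 at n=20.

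**Carry-over into weight gain.** Bias left = 2 kg × (1 − share of the error common to later weights): 2, 1 or 0 kg for a share of 0, 50% or 100%.

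**Yes/no items.** With true kappa 0.61 and equal margins at prevalence p, both sources are negative with probability q = (1−p)² + 0.61p(1−p). Kappa is undefined when every woman falls in that cell (or, negligibly often, every woman is positive in both), so with probability close to qⁿ. At p = 5%, q = 0.9025 + 0.0290 = 0.9315, giving 49% at n=10 and 24% at n=20. Other values at n=10/n=20 are 76%/57% (p = 2%), 23%/5.5% (10%) and 4.8%/0.2% (20%).

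**The case against.** The best case against is that a choice of statistic per variable is ordinary analysis-plan detail. Biostatisticians will be consulted, the item list is only indicative, and nothing says kappa will be applied to weight or due date or that nothing else will be reported. That would excuse silence. But the protocol does state a method for the baseline data and attaches a label to it, and read literally this covers the continuous baseline items. Weight gain in delivered women is less clearly covered, since it is not a baseline item.

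Several narrower objections stand as limits:
- Kappa does respond to error size (BMI-class kappa falls from 0.94 to 0.84 with a 2 kg bias). What it lacks is units and direction.
- Class agreement has some use of its own, because section 2.2 plots women on the appropriate IOM chart and the height footnote in section 4.4.2.1 refers to BMI.
- A difference is a reporting error only if the recorded pre-pregnancy weight is right, which the protocol does not establish.
- No consequence has been shown for age.
- An error shared fully with later self-entered weights cancels out of weight gain.
- With so few women, the mean difference is imprecise too. Its interval would at least show that; the label does not.

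**Conclusion.** The concern holds, as a minor one. That kappa shows neither direction nor error in kilograms or days follows from its definition and needs no assumed figure. The sizes rest wholly on the assumed weight, height and error distributions: at n=20, a 2 kg under-report would be labelled substantial to excellent in about 98% of samples on BMI classes, and a 3 kg under-report in about 90%. It matters most for pre-pregnancy weight, because of its link to a primary outcome, and then only to the extent that later weights do not share the error. No stated decision depends on the label, so what is affected is what the pre-launch check can show about self-report. The undefined-kappa point for yes/no items is secondary and depends on a prevalence the protocol does not give.

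**What to change.** In section 4.4.6, state: *For age, pre-pregnancy weight, estimated due date and, in women who have delivered, weight gain, we will report the mean difference (self-report minus record) with its 95% CI and 95% limits of agreement. For categorical items we will report raw percent agreement alongside kappa where it is defined, with 95% CIs. With N=10-20 this comparison is descriptive.*

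The cost is three sentences and a little more analysis of the same records, with no extra testers or data. The single headline label is given up for the continuous items. The change does not cure the small sample: at n=10 with a 3 kg error SD, a 2 kg bias would still be distinguished from zero in only 46% of samples.

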5.1. REGISTRY DATA STORAGE

Under a contract with Lockheed Martin, PregSourceSM will use a web-based, patient opt-in registration system developed by PatientCrossroads, Inc., San Mateo, California, for DS-Connect® and other registries. PatientCrossroads will track participant enrollment, capture data, and deliver appropriate summary information based on entered data via a secure web portal, using MySQL Server as the back end relational database.

Lockheed Martin will work with PatientCrossroads to ensure that the system is compliant with the Health Insurance Portability and Accountability Act of 1996 (HIPAA) and with the Federal Information Security Management Act of 2002 ("FISMA", 44 U.S.C. §3541). Security features target multiple levels, including the data element (e.g., restricted access to fields), user (e.g., password authentication access), application (e.g., role-based access to features, access audit trails), and hosting services (e.g., firewall, secure sockets layer). These features ensure access and audit control, data integrity, user authentication, and transmission security.

All server requests are transmitted over Secure Sockets Layer (SSL). All servers have multiple layers of data and access protection: (1) A dedicated, managed Cisco router firewall, (2) A redundant array of independent disk (RAID) Level 5 is used to ensure that data will not be lost if a hard drive fails between backups, (3) A system level backup is performed nightly, retained for 2 weeks, and stored in the data center, (4) a database level backup is performed nightly, retained for 2 months, and stored at the data center.

5.2. DATA SHARING

Researchers may request data from the registry to analyze it for research purposes, such as to determine the prevalence of clinical manifestations and/or estimate numbers of participants who may be eligible for approved clinical studies or trials. The Operations Committee or its designees will review these requests. If approved, researchers may be given access to de-identified data only via the Website's Professional Portal which will be launched in the future.

5.3. DATA DISPOSITION

On a regular schedule (not less often than once every 5 years) and when the registry stops accepting new participants and new data from existing participants, PregSourceSM will submit de-identified data to a NICHD data repository such as DASH (Data and Specimen Hub) for future researchers to access and analyze.

Once a participant has completed the registration and consent process, she will be able to view summaries of the de-identified data from all participants. This access will allow her to see how she compares with other similar participants.

5.4. REGISTRY SAMPLES STORAGE AND DISPOSITION

PregSourceSM does not plan on collecting biological samples at this time.

5.5. ADDITIONAL CONSIDERATIONS

5.5.1. Research with Investigational Drugs or Devices

PregSourceSM will not be conducting research with any investigational drugs or devices.

5.5.2. Gene Therapy

PregSourceSM will not be using any gene therapy.

SECTION 6. POTENTIAL RISKS AND BENEFITS

